In a local study, more than 30% of type A aortic dissection (TAAD) patients were misdiagnosed in the ED. Among these misdiagnosed patients, many presented with normal blood pressure and relatively mild signs and symptoms, resulting in their triage in lower categories.(9) Additionally, the absence of a POCUS ultrasound exam was identified as an

independent factor associated with misdiagnosis in the ED.(9) Therefore, performing a POCUS scan could help identify TAA and TAAD patients in the ED even when they have a low pretest probability.

Aim

This study aims to evaluate the prevalence of TAA in hypertensive patients identified in the ED using POCUS.

Objectives

- 1. To investigate the number of hypertensive patients presenting to the ED with a rtic diameter \geq 4.5 cm as indicated by POCUS
- 2. To evaluate the number of patients with confirmed TAA as verified by CTA
- 3. To evaluate the agreement of aortic diameter measurement between CTA and POCUS

Hypotheses

1. POCUS can identify TAA by measuring the aortic diameter.

Methodology

This prospective cohort study is coordinated by the Accident and Emergency Medicine Academic Unit of the Chinese University of Hong Kong (CUHK) in collaboration with the Department of Surgery and the Department of Medicine and Therapeutics of CUHK. The investigators will carry out this study in the accident and emergency department at Prince of Wales Hospital (PWH). PWH serves a population of 1.6 million people in the New Territories of Hong Kong and is the main teaching hospital of CUHK. The investigators will be trained for POCUS before the commencement of the study and the images will be audited by an echocardiologist.

Inclusion and exclusion criteria for participants

Inclusion criteria:

- 1. Adult patients aged \geq 18 years attending the ED during the study period
- 2. Known history of hypertension or newly diagnosed hypertension in the ED

Exclusion criteria:

- 1. Known history of aortic aneurysm or dissection
- 2. Previous thoracic aortic interventions or endovascular stenting
- 3. Patients in cardiopulmonary resuscitation

- 4. Traumatic patients
- 5. Patients refuse to participate the study

Sample size calculation

According to previous studies, the estimated prevalence of TAA in hypertensive patients in a clinic was 7.5% and the area under the curve for POCUS detecting aortic dilation was 0.857.(5, 10) With a confidence level of 95% and margin of error of 5%, 1186 patients will be needed.(11)

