To ensure that this study has enough participants after accounting for a 20% inadequate visualization of the POCUS image, the investigators will need to recruit 1483 participants. The investigators target to complete the recruitment within 12 months.

Data collection

The investigators trained with POCUS will recruit and screen patients in the ED during the study period using an ultrasound device throughout the study and all images will be stored for regular review by an echocardiologist.

POCUS screening will be conducted to measure the maximum diameters at end diastole of the aortic root, ascending aorta, aortic arch, and descending thoracic aorta. The internal diameter will be measured perpendicular to the axis of blood flow and leading edge to leading edge in accordance with the guidelines set forth by the American College of Cardiology.(12) Measurements of the aortic root and ascending aorta will be taken using parasternal long-axis views, while the aortic arch will be assessed from the suprasternal view. The descending thoracic aorta will be examined using modified apical 2-chamber and subcostal views. The investigators will also specifically look for an intimal flap, pericardial effusion and aortic regurgitation.

The investigators will inform the emergency physicians under the following conditions:

- 1. patient has an aortic diameter \geq 5cm
- 2. patient has an intimal flap, pericardial effusion or moderate aortic regurgitation

If physicians identify a clinical possibility of TAA, these patients will be referred to cardiothoracic surgeons. If there is a suspicion of acute aortic syndrome, the ED physicians will consult cardiothoracic surgeon urgently \pm CTA in the ED as usual practice.

Relevant clinical data (such as past medical history, laboratory results, operation records etc.) will also be collected. In addition, the investigators will follow up with the patients for 28 days to monitor mortality and any advanced imaging performed outside the ED.

Outcome measurement

The primary outcome is the number of patients with TAA (a maximum aortic diameter of \geq 4.5 cm and/or \geq 50% localized enlarged diameter relative to the adjacent normal segment as indicated by POCUS).

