The secondary outcomes include the number of patients with confirmed TAA as verified by CTA, BMI for all participants, the number of CTA scans conducted for TAA confirmation, the number of surgical interventions performed among TAA patients, the ICU admission rate, ICU length of stay, hospital length of stay and mortality, proportion of adequate visualisation of POCUS studies obtained, agreement of aortic diameter measurement between CTA and POCUS, and signs and symptoms of TAA patients presenting to the ED. In addition, the investigators will assess the 28-day all-cause mortality and any advanced imaging done outside the ED for evaluating the aorta.

Statistical analysis

Patients with a maximum aortic diameter ≥ 4.5 cm and/or $\geq 50\%$ localized enlarged diameter relative to the adjacent normal segment are regarded as TAA while those with an aortic diameter < 4.5 cm are regarded as non-TAA. Comparison of baseline characteristics and aortic size measurements will be made between these two groups of patients. Categorical variables will be compared with Chi square test or Fisher's exact test. Continuous variables will be compared using Student's t-test or Mann-Whitney U test, based on the results of the Shapiro-Wilk W test. Binary logistic regression analysis will be used to identify the risk factors that associated with TAA independently and to predict the presence of TAA. Variables with a p < 0.2 from the univariate analysis will be included in the stepwise logistic regression model. In patients who underwent a CTA, the investigators will assess the agreement of aortic diameter measurements between CTA and POCUS using Bland-Altman analysis. All statistical analyses and visualisations will be done using R or Prism GraphPad.(13, 14) A significance level of 0.05 will be considered statistically significant.

Patients with missing data on certain variables will be removed from that particular analysis. POCUS studies with inadequate visualisation of all views will be discarded.

Ethics

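### The logistic model is given a predictive purpose, but the protocol's building rule uses unshrunk coefficients from an uncapped candidate list, so with about 89 expected events its predictions will on average be too extreme

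*Protocol*

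**What the plan says.** The Statistical analysis section of the protocol gives one model two tasks: "Binary logistic regression analysis will be used to identify the risk factors that associated with TAA independently and to predict the presence of TAA". The second task, "and to predict the presence of TAA", is the one at issue here. The section then sets the selection rule: "Variables with a p < 0.2 from the univariate analysis will be included in the stepwise logistic regression model". Patients with missing values drop out of the analysis concerned. On software it says "All statistical analyses and visualisations will be done using R or Prism GraphPad". No list or maximum number of candidate variables is given, and no penalisation, resampling or performance measure is named for this model.

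The Sample size calculation states that "the estimated prevalence of TAA in hypertensive patients in a clinic was 7.5" (per cent), that "the area under the curve for POCUS detecting aortic dilation was 0.857", and "With a confidence level of 95% and margin of error of 5%, 1186 patients will be needed". The target rises to 1483 after "accounting for a 20% inadequate visualization of the POCUS image".

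Prediction is not mentioned in the Aim, the Objectives, the Hypotheses or the Outcome measurement section. The AUC of 0.857 describes ultrasound detecting dilation. It is not a property of the logistic model.

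**The concern.** Identifying associated factors and predicting who has TAA are different tasks. For prediction, coefficients estimated by ordinary maximum likelihood fit the noise of the sample as well as the signal. Applied to new patients, they put high risks too high and low risks too low (calibration slope below 1), and the AUC in the fitting data overstates the AUC elsewhere.

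The fewer the events per candidate, the larger the effect. The candidate pool here is open: the protocol collects medical history, laboratory results and more, along with BMI and presenting features, and any baseline variable compared between groups could enter the screen.

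This is separate from the usual complaint about stepwise selection. A model with all variables fixed in advance has the same problem, so replacing the selection rule alone would not cure it. If predicted probabilities or an AUC were reported from the model as the protocol builds it, they would tend to flatter it.

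**Working it through.** **Inputs from the protocol.** Evaluable N = 1186, recruited N = 1483, prevalence 7.5%, AUC for ultrasound 0.857, 95% confidence, margin 0.05, 20% inadequate images.

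**Step 1: the protocol's figures reproduce.** With n1 = 1186 x 0.075 = 88.95 cases and n0 = 1097.05 non-cases, the Hanley-McNeil terms are 0.857/(2 - 0.857) = 0.7498 and 2 x 0.857²/(1 + 0.857) = 0.7910. The variance is [0.857 x 0.143 + 87.95 x (0.7498 - 0.7344) + 1096.05 x (0.7910 - 0.7344)]/(88.95 x 1097.05) = 0.00065. The half-width is 1.96 x √0.00065 = 0.050, as stated. Then 1186/0.8 = 1483.

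**Step 2: events.** 1186 x 0.075 = 88.95, about 89. If every recruited patient were evaluable it would be 1483 x 0.075 = 111. Complete-case deletion lowers the number in the model. The 7.5% comes from a clinic, so the ED figure may lie on either side.

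**Step 3: expected shrinkage.** The usual heuristic is LR/(LR + k), where k is the number of candidate parameters and LR the model likelihood ratio. The protocol gives neither k nor the model's true AUC, so both are assumed. With N = 1186 and 7.5% prevalence, LR is about 43.3 at a true AUC of 0.70 and 109.3 at 0.80.

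| k | true AUC 0.70 | true AUC 0.80 |
|---|---|---|
| 5 | 0.90 | 0.96 |
| 10 | 0.81 | 0.92 |
| 20 | 0.68 | 0.85 |
| 30 | 0.59 | 0.79 |

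**Step 4: simulation.** N = 1186, 7.5% prevalence, 100 data sets per scenario, each model tested on a population of 40,000. Assumed: independent predictors, half continuous and half binary, 3 to 5 of them real, true AUC 0.70 or 0.80. The protocol's rule was taken as the p < 0.2 screen followed by backward elimination at 0.05. Cells show mean calibration slope, then AUC optimism, across the two AUC values.

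| Candidates | All variables kept | Screened and stepwise |
|---|---|---|
| 5 | 0.93-0.95; 0.01-0.015 | 0.96-0.97; 0.005-0.01 |
| 10 | 0.83-0.90; 0.02-0.04 | 0.89-0.94; 0.015-0.03 |
| 20 | 0.70-0.80; 0.05-0.06 | 0.83-0.90; 0.02-0.035 |
| 30 | 0.57-0.71; 0.07-0.10 | 0.75-0.87; 0.03-0.05 |

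Every mean slope is below 1. For the same candidate list, the model that keeps all variables is more overfitted than the selected one, so selection is not the sole cause. In single data sets the slope was below 1 in 64-78% of runs with 5 candidates and 88-100% with 30.

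**Step 5: weaker predictors.** Four real predictors were assumed, with log odds ratios per SD of 0.40, 0.30, 0.25 and 0.20, and the rest noise. Screened and stepwise slopes were 0.78-0.79 with 15 candidates and 0.68-0.73 with 25. The spread between runs is simulation error, and about 0.73 is a fair lower figure. Apparent AUC was about 0.67-0.68 against a true 0.62-0.635. With effects 50% stronger the slopes were 0.84-0.88.

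**Step 6: meaning for one patient.** Re-centring on the average risk, a stated 20% corresponds to logit(0.075) + slope x [logit(0.20) - logit(0.075)] = -2.512 + slope x 1.126. This gives 19.1% at slope 0.95, 18.1% at 0.89 and 15.6% at 0.73.

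**The case against.** The strongest objection is that this is an omission. Validation and shrinkage of a secondary regression are commonly left to a statistical analysis plan, which is not at hand. That stands in part: it cannot be said that the model will never be validated, only that the protocol does not provide for it. It does not dispose of the point, because the protocol itself states the predictive purpose and prescribes the building rule, and that rule serves the purpose badly.

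Second, 89 events do not by themselves make the predictions poor. This stands. With about 5 strong candidates the effect is trivial, and it becomes material only with longer lists or weaker predictors. The protocol secures neither a short list nor strong predictors.

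Third, a reader might infer that the study will publish inflated risks or an inflated AUC, or that the model is meant to choose whom to scan. The documents support neither. No AUC, risk score or predicted risk is promised for this model, and enrolled patients are to be scanned by protocol, not selected for scanning by a model. Nor was the sample size chosen with this model in mind.

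**Conclusion.** The point holds in a limited form. As the protocol is written, an unpenalised model chosen from an uncapped list is to be used for prediction with about 89 expected events. On average its predictions will be too extreme and any apparent discrimination too high, with or without stepwise selection.

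The direction is firm on average. The size is conditional on the assumed number and strength of candidates. It runs from negligible (slope about 0.95, AUC optimism about 0.01, with 5 strong candidates) to material (slope about 0.73-0.89, optimism about 0.03-0.05, for the screened and stepwise model with 15 to 25 candidates). It is worse still if all of 25 candidates are kept. The event count also assumes that the clinic prevalence carries over to the ED.

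Only a secondary analysis is touched. The prevalence aim, the primary outcome, the sample size and the comparison of CTA with ultrasound are not. The change is worth making before analysis starts, but the study does not depend on it.

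**What to change.** Choose one of two changes to the Statistical analysis section.

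- **Keep the predictive purpose.** State that the entire building procedure, including the screen and the selection, will be repeated in at least 500 bootstrap samples in R; that any AUC and calibration slope reported will be corrected for optimism; and that coefficients will be multiplied by the corrected slope, or fitted by penalised likelihood, before any predicted probability is given. In a small simulation check the correction recovered the truth. With 15 candidates and selection, corrected AUC was 0.629 against 0.628 and slope 0.76 against 0.76. With 8 fixed variables, AUC was 0.645 against 0.642 and slope 0.82 against 0.81.
- **Drop it.** Delete "and to predict the presence of TAA" and claim associations only. This matches the stated aim and objectives.

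The first costs a sentence or two and some analysis time in software already named, and the reported performance will look slightly less favourable. The second costs only the predictive claim. Neither needs more patients or data.

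### Objective 3 measures CTA-POCUS agreement in everyone who had a CTA, so CTAs prompted by a large POCUS diameter can make an unbiased POCUS appear to over-measure in the triggering segment

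*Protocol*

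**What the plan says.** Objective 3 in the Protocol is "To evaluate the agreement of aortic diameter measurement between CTA and POCUS". Statistical analysis fixes both the set and the method: "In patients who underwent a CTA, the investigators will assess the agreement of aortic diameter measurements between CTA and POCUS using Bland-Altman analysis". The reason for the CTA plays no part.

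CTA is neither done in all participants nor allocated at random. The routes to it are these:

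- **Data collection, notification.** "The investigators will inform the emergency physicians under the following conditions": a diameter of 5 cm or more, or one of three findings that are not diameters (a flap, an effusion, valve regurgitation).
- **Data collection, next step.** "If physicians identify a clinical possibility of TAA, these patients will be referred to cardiothoracic surgeons". Separately, "If there is a suspicion of acute aortic syndrome, the ED physicians will consult cardiothoracic surgeon urgently", with CTA in the ED left to usual practice.
- **Outcome measurement.** The secondary outcomes include "the number of CTA scans conducted for TAA confirmation", so some CTAs are expected to follow from the POCUS result. They also include "any advanced imaging done outside the ED for evaluating the aorta".
- **Safety Management.** Incidental aortic abnormalities go to the attending physician, with no diameter named, so readings below 5 cm may also lead to CTA.

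POCUS is to "measure the maximum diameters at end diastole of the aortic root, ascending aorta, aortic arch, and descending thoracic aorta", so each patient can supply up to four pairs. The Protocol does not say whether agreement is assessed by segment or on the largest diameter.

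**The concern.** One of the two measurements being compared helps to decide who is compared. A POCUS reading is the true diameter plus error. Patients sent for CTA because the reading was high have, on average, a positive error in that segment; the CTA carries no such selection. This is regression to the mean, and a Bland-Altman analysis does not remove it.

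CTAs ordered for suspected acute aortic syndrome, or for the non-diameter findings, are not selected on diameter error and dilute the effect. CTAs outside the ED can be of either kind, since referral for possible TAA may lead to a confirmatory scan there.

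At stake is the reading of Objective 3. A positive mean difference could be taken as POCUS over-measuring when part of it reflects who was scanned. If the reason for each CTA is not recorded, the two cannot be told apart afterwards.

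**Working it through.** **The Protocol's own figure.** Sample size calculation gives 1186 evaluable patients. The Hanley-McNeil standard error with AUC 0.857 and 7.5% cases gives a 95% half-width of 0.04998 at N = 1186, which matches; 1186/0.8 = 1482.5, rounded up to 1483, also matches. That calculation is for an AUC interval and says nothing about agreement. It is used here only for N.

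**Inputs.** From the Protocol: 1186 readable scans, 7.5% at 4.5 cm or more, and the 5 cm notification level. Assumed, because the Protocol does not give them: no true POCUS bias; true-diameter SD (sdT) 0.5 cm; CTA error SD 0.1 cm; POCUS error SD (sdE) 0.1 to 0.4 cm; CTA in a share ph (80% or 30%) of patients at or above the trigger c, and in a share pl (5% or 1%) of the rest.

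**Formulas, for the triggering segment.**

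- s = √(sdT² + sdE²); μ = 4.5 − 1.44·s, so that 7.5% of readings are at least 4.5 cm
- a = (c − μ)/s; Q = 1 − Φ(a); K = pl + (ph − pl)·Q
- Pairs = 1186·K
- Shift in mean POCUS − CTA = (ph − pl)·(sdE²/s)·φ(a)/K
- Variance of differences = sdE² + 0.1² + (sdE²/s)²·(ph − pl)·a·φ(a)/K − shift²
- 95% half-width = t × SD/√pairs

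**Worked case** (c = 5, sdE = 0.3, ph = 0.80, pl = 0.01). s = 0.583, μ = 3.661, a = 2.297, Q = 0.0108, φ(a) = 0.0285.

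- K = 0.01 + 0.79 × 0.0108 = 0.0185, giving 22 pairs
- Shift = 0.79 × (0.09/0.583) × 0.0285/0.0185 = 0.188 cm
- SD of differences = 0.362 cm; half-width = 2.08 × 0.362/√22 = 0.16 cm

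**All settings: shift / 95% half-width, cm**

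| Trigger | CTA at or above / below trigger | sdE 0.1 | sdE 0.2 | sdE 0.3 | sdE 0.4 |
|---|---|---|---|---|---|
| 5 cm | 80% / 5% | 0.006 / 0.035 | 0.024 / 0.056 | 0.057 / 0.082 | 0.106 / 0.110 |
| 5 cm | 80% / 1% | 0.020 / 0.069 | 0.083 / 0.112 | **0.188 / 0.161** | **0.328 / 0.208** |
| 5 cm | 30% / 5% | 0.002 / 0.036 | 0.009 / 0.058 | 0.021 / 0.083 | 0.040 / 0.110 |
| 5 cm | 30% / 1% | 0.010 / 0.081 | 0.041 / 0.131 | 0.097 / 0.191 | 0.178 / 0.256 |
| 4.5 cm | 80% / 5% | 0.020 / 0.025 | **0.074 / 0.040** | **0.154 / 0.059** | **0.250 / 0.078** |
| 4.5 cm | 80% / 1% | **0.032 / 0.031** | **0.120 / 0.048** | **0.249 / 0.067** | **0.404 / 0.086** |
| 4.5 cm | 30% / 5% | 0.010 / 0.031 | 0.038 / 0.051 | **0.079 / 0.074** | **0.129 / 0.098** |
| 4.5 cm | 30% / 1% | 0.025 / 0.047 | **0.096 / 0.075** | **0.200 / 0.107** | **0.323 / 0.141** |

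Bold marks a shift larger than the half-width: 2 of 16 settings at 5 cm, 12 of 16 at 4.5 cm.

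**All four segments pooled** (simulation, 5 cm trigger on the largest segment, 80% CTA at or above it, sdE 0.2 to 0.4): 0.005 to 0.024 cm with 5% otherwise, and 0.018 to 0.082 cm with 1% otherwise. The non-triggering segments show essentially no shift.

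**Effect of separating the CTAs** (5 cm trigger, sdE 0.2/0.3/0.4). Diameter-prompted pairs: shift +0.20/+0.41/+0.64 cm. The remaining pairs: within 0.01 cm of zero (with a 4.5 cm trigger, at most 0.04 cm below zero).

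**The case against.** **The Protocol does not say that a single pooled analysis will be the only one, or that the mean difference will be read as bias.** This is fair as to interpretation and stratification, which a SAP may settle. It does not remove the point: the Protocol itself states the analysis set, and a SAP that follows it inherits the selection.

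**The route from diameter to CTA is indirect.** A reading of 5 cm or more leads to notification, possible TAA leads to referral, and CTA is named only where acute aortic syndrome is suspected. This stands as to size. The 80% figure has no basis in the document, and at 30% with a 5 cm trigger the shift never exceeds the half-width. That some CTAs follow from the POCUS result is nonetheless shown by the outcome that counts confirmatory scans. A 4.5 cm trigger rests only on the general sentence in Safety Management.

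**Separating the CTAs helps little.** Partly right. The diameter-prompted pairs are few and more shifted than the pooled set, and the others include few large aortas. What the separation does give is one nearly unshifted estimate of bias and a label on the other.

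A reader might go further and treat every CTA as selected on size, which would put the shift at +0.20 to +0.64 cm with a 5 cm trigger (true SD 0.5 cm, error SD 0.2 to 0.4 cm). The document does not support that, because it names routes to CTA that do not depend on diameter.

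**Conclusion.** The point holds as a minor one. The stated analysis set mixes CTAs prompted by the POCUS diameter with CTAs that were not, so the mean difference in the triggering segment can be positive without any POCUS bias. The size cannot be known from the Protocol. On the assumptions above it runs from negligible to 0.33 cm with a 5 cm trigger, usually inside the confidence interval, and up to 0.40 cm, often outside it, if readings from 4.5 cm prompt CTA. Pooling all four segments brings it to at most about 0.08 cm with mixed routes and a 5 cm trigger.

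It should not be inferred that Objective 3 is certain to be materially biased: most of the 5 cm settings say otherwise. Nor does the point touch the primary outcome, which is a count defined on POCUS alone and uses no CTA.

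**What to change.** Record prospectively, for each CTA in or outside the ED, why it was ordered and, if the POCUS diameter was the reason, which segment triggered it. Counting CTAs done to confirm TAA already requires part of this classification.

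Run Bland-Altman by segment. Keep the overall result, and report separately:

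- (a) pairs whose CTA was prompted by the POCUS diameter, labelled as conditional on a high reading;
- (b) pairs whose CTA was ordered for reasons unrelated to it.

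Assign outside-ED CTAs by recorded reason, not by location, and put a CTA with both reasons in (a). State that neither the pooled nor the set (a) mean difference is to be interpreted as POCUS measurement bias.

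The cost is one or two data fields and a few sentences, with no change to recruitment or care. The statistical price should be stated. With a 5 cm trigger, set (a) may hold only about 3 to 5 pairs (30% scanned) or 7 to 13 (80%). Set (b) may hold about 11 to 59 pairs across both triggers. With a 5 cm trigger only about 6 to 7% of set (b) read 4.5 cm or more, so about 4 of 59 or 1 of 12; with a 4.5 cm trigger fully applied there are none. Set (b) therefore estimates bias mainly at smaller diameters, and neither set gives precise agreement near 4.5 to 5 cm.

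### The rule that discards scans with no adequate view has no exception, so taken literally it inflates the scan-adequacy outcome and leaves unclear whether those patients stay in outcomes that need no POCUS diameter

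*Protocol*

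**What the plan says.** The last paragraph of Statistical analysis in the protocol gives two rules. The first concerns patients: "Patients with missing data on certain variables will be removed from that particular analysis". The second concerns scans: "POCUS studies with inadequate visualisation of all views will be discarded". The second rule carries no exception for any outcome.

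Outcome measurement lists among the secondary outcomes the "proportion of adequate visualisation of POCUS studies obtained". Several other listed outcomes do not depend on a readable scan: CTA-confirmed TAA (also Objective 2), "BMI for all participants", ICU and hospital stay, and mortality. On the 28-day outcomes it adds that "the investigators will assess the 28-day all-cause mortality and any advanced imaging done outside the ED for evaluating the aorta". Only BMI has its population stated.

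Two other places bear on the point. Sample size calculation raises recruitment for failed imaging: "accounting for a 20% inadequate visualization of the POCUS image, the investigators will need to recruit 1483 participants". Data collection has all images stored, and says that "the investigators will follow up with the patients for 28 days to monitor mortality and any advanced imaging performed outside the ED". Neither the storage nor the follow-up is limited to patients with an adequate scan.

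**The concern.** The adequacy outcome counts POCUS studies, and the discard rule removes POCUS studies. A proportion of adequate studies means something only if the inadequate ones are in the denominator. An analyst who discards the total failures first and then computes the proportion gets a figure that is too high. How often an image can be obtained in the ED is part of whether POCUS can serve as a screen, so this outcome should not be left to the order in which two steps are carried out.

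The second issue is how far the rule reaches. CTA-confirmed TAA, BMI, ICU and hospital stay, and the 28-day outcomes need no POCUS diameter. If discarding the scan is taken to discard the patient, a patient whose scan failed and whose CTA showed a TAA would drop out of Objective 2. That is a case the screen did not find, and a screening study should show it.

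**Working it through.** **1. The plan's own figures.** Inputs from Sample size calculation: AUC A = 0.857, prevalence 0.075, 95% confidence, margin 0.05, 20% inadequate visualisation.

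Hanley-McNeil standard error, with n1 = 0.075N and n0 = 0.925N:

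SE² = [A(1−A) + (n1−1)(Q1−A²) + (n0−1)(Q2−A²)] / (n1·n0), where Q1 = A/(2−A) and Q2 = 2A²/(1+A).

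At N = 1186, SE = 0.02550 and 1.96 × SE = 0.04998. This is the smallest N with a half-width of at most 0.05, so 1186 reproduces. Inflation: 1186/0.8 = 1482.5, rounded up to 1483, which also reproduces. The sample size is not in question here.

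**2. Scans planned to be inadequate.** 1483 − 1186 = 297. Adequacy over all scans attempted: 1186/1483 = 80.0%.

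**3. Adequacy if total failures leave the denominator.** The discard rule covers scans in which every view fails. The protocol does not say what share of the 297 that would be, so the share s is an assumption. Reported adequacy = 1186 / (1483 − 297s), with the number discarded rounded to a whole scan.

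| Assumed share s | Scans discarded | Denominator | Reported adequacy |
|---|---|---|---|
| 0% | 0 | 1483 | 80.0% |
| 25% | 74 | 1409 | 84.2% |
| 50% | 148 | 1335 | 88.8% |
| 100% | 297 | 1186 | 100% |

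The bias is upwards for any share above zero. It reaches 100% only if every inadequate scan fails in all views.

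**4. POCUS TAA under two denominators (upper bound, s = 100%).** Expected cases among adequate scans: 0.075 × 1186 = 88.95, about 89. Per patient with an adequate scan: 89/1186 = 7.5%. Per patient scanned: 89/1483 = 6.0%.

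**5. TAA among patients with an inadequate scan.** If their prevalence were also 7.5%, 297 × 0.075 gives about 22 cases, again an upper bound for the discarded group. If 10% or 5% of recruits were discarded (148 or 74), it would be about 11 or 6. How many of these would have a CTA cannot be derived from the protocol.

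**6. How far the discard rule reaches.** Three features point to exclusion beyond the diameter analyses:
- The missing-data rule just before it already keeps a scan without a diameter out of any analysis that needs one, so the discard sentence either adds something or is redundant.
- Ethics uses the same verb for complete removal, both after death before consent and after withdrawal.
- The inflation to 1483 treats inadequate scans as not counting towards 1186.

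Three features point the other way:
- The object discarded is the scan, and patients are dealt with in a separate sentence.
- Where Ethics means that data are to be erased, it names the data.
- Image storage and 28-day follow-up are not limited to adequate scans.

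The text supports either reading.

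**The case against.** The strongest reply is that the sentence discards scans and not patients. Read with the missing-data rule, it may mean only that an unreadable scan gives no diameter and the patient leaves the analyses that need one. Listing adequacy as an outcome also suggests that attempted scans will be counted before any are set aside. Leaving unreadable scans out of the POCUS diameter results and the Bland-Altman analysis is unavoidable and correct. The primary outcome is a count of TAA on POCUS, and discarding scans that could not have been positive does not change it. Denominators for secondary outcomes are often left to an SAP, which is not at hand.

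Much of this stands. A reader might infer that adequacy must come out at 100%. It need not: the rule covers only failure of all views, Data collection plans several views, and partly failed scans are kept. A reader might also infer that every one of these outcomes is specified for all participants and therefore contradicts the rule. The protocol attaches that phrase to BMI alone and leaves the other populations unstated. Nor does the protocol say that patients with failed scans are lost, and nothing in it links an unreadable scan to death, so no size can be put on a mortality bias.

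What the reply does not remove is the conflict over adequacy. The point does not rest on a missing denominator. The protocol states a rule without exception, and that rule acts on the very units its own outcome counts. Counting first and discarding afterwards is a sensible reading, but it is not written down, and two analysts could report different figures from the same data.

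**Conclusion.** The point holds in two parts of different strength. Firmly: followed literally, the discard rule biases the adequacy proportion upwards, from 80% to between about 84% and 100% at the planned failure rate, if between a quarter and all of the inadequate scans fail in every view. Those shares are assumed, so 297 scans and 100% are upper bounds and not expectations. Less firmly: the rule can be read as removing the same patients from CTA-confirmed TAA, BMI, ICU and hospital stay, and the 28-day outcomes. This would conflict with the stated population for BMI and could hide a TAA found on CTA after a failed scan. The text leaves this open, and the stronger claim that these patients will be lost is not supported.

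The contrast of 7.5% with 6.0% comes from the choice of denominator. The lower figure is a detection yield among everyone scanned and should not be presented as the prevalence. Because the rule changes what the adequacy, CTA-confirmed and yield results show, it should be corrected, but it does not affect the sample size or the primary count.

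**What to change.** In Statistical analysis, replace the instruction to discard these studies with wording such as: *will be recorded as inadequate and left out only of analyses that need a POCUS diameter; the participant stays in the adequacy denominator and in all outcomes that need no POCUS diameter.*

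Add two reporting items:
- POCUS TAA per patient with an adequate scan and per patient scanned, each labelled as such.
- The number of CTA-confirmed TAA cases among patients whose scan was inadequate.

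The cost is one changed sentence and two reported lines. No further data are needed, because image storage, clinical data collection and 28-day follow-up are already planned without restriction to adequate scans, and 1186 and 1483 stay as they are. The drawback is that the yield per patient scanned will look less favourable than the yield among patients who could be imaged.
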